2.7. Protocol Deviations

Protocol deviations are collected from time of informed consent until the last study visit. Protocol deviations are defined as any variation from the protocol, including enrollment of a subject who did not meet all inclusion and exclusion criteria and failure to perform the assessments and procedures within the required time frame. Protocol deviations will be categorized into types of deviations (concomitant medication, inclusion/exclusion, informed consent, procedures/assessments, randomization, serious adverse event reporting and adverse events of special interest, study treatment administration/dispensing/compliance, and study visits) and classified as major or minor.

The Sponsor or designee will be responsible for producing the final protocol deviation file.

2.8. Subgroup analyses

Subgroup analyses will be conducted for the FDA and EMA primary efficacy endpoints. The purpose of the subgroup analyses is to assess the consistency of treatment effect across potential or expected prognostic factors. Additional subgroup analyses may be also be conducted.

The list of subgroups will be finalized prior to database lock but will include:

- Sex (male versus female)
- Race (white versus non-white and Asian versus non-Asian)
- Age category (< 65 years versus ≥ 65 years)
- Geographic region (United States/South America, Europe/Israel/Turkey, Asia-Pacific (excluding China/Taiwan), China/Taiwan)
- Diagnosis at randomization (candidemia only versus IC)

- Final Diagnosis (candidemia only versus IC: progression from candidemia only to IC will be determined based on the radiological and/or tissue/fluid culture assessment through Day 14)
- APACHE II score/ANC at Screening (APACHE II score ≥ 20 OR ANC < 500 cells/ μ L versus APACHE II score < 20 AND ANC ≥ 500 cells/ μ L)
- APACHE II score at Screening (≥ 20 , < 20 , 10-19, < 10)
- ANC at Screening (< 500 cells/ μ L versus ≥ 500 cells/ μ L)
- Timing of culture used to document the *Candida* infection:
 - Positive culture at randomization definition 1: Subjects with a culture from blood drawn within 12 hours prior to randomization or within 72 hours after randomization, OR a culture from another normally sterile site obtained within 48 hours prior to randomization or within 72 hours after randomization; and
 - Positive culture at randomization definition 2: Subjects with a culture from blood drawn within 12 hours prior to randomization or within 72 hours after randomization, OR a culture from another normally sterile site obtained within 96 hours prior to randomization or within 72 hours after randomization

3. GENERAL STATISTICAL METHODS

3.1. Sample Size Justification

The study is designed to show non-inferiority (NI) in the primary efficacy outcome of ACM at Day 30 (FDA) in the mITT population and global cure rate (EMA) at Day 14 following the first dose of test article in the mITT population. An NI margin of 20% will be used for the primary analyses. The NI margin was based on an analysis of studies where patients received no treatment or inadequate treatment, and the high unmet medical need in patients with candidemia and/or IC.

Sample size justification for the Primary Efficacy Outcome FDA (Day 30 ACM): For the FDA endpoint of ACM, assuming 85% of subjects will be evaluable for the mITT population, using a 20% NI margin, one-sided alpha of 0.025, an ACM rate of 20% in both treatment groups, 1:1 randomization, and the sample size methodology based on a continuity corrected Z-statistic, a total of 184 subjects in the mITT population provides 89.7% power to show NI.

Sample size justification for the Primary Efficacy Outcome EMA (Global cure): Using a 20% NI margin, one-sided alpha of 0.025, 80% power, 1:1 randomization, a global cure rate of 70% in both the Rezafungin for Injection and caspofungin groups, and the sample size methodology based on a continuity corrected Z-statistic, a total of 184 subjects (92 subjects in each treatment

group) are required in the mITT population. Assuming 85% of subjects will be evaluable for the mITT population, a total of approximately 218 subjects will be randomized.

Thus, a total of 218 randomized subjects provide sufficient power for the primary efficacy analyses for both the FDA and the EMA in the mITT population. A summary of the sample size calculations and assumptions is provided in the **Table 3-1** below:

Table 3-1: Sample Size and Power Calculations

	Primary Efficacy Outcome FDA (Day 30 ACM)	Primary Efficacy Outcome EMA (Global Cure)
Population	mITT	mITT
Outcome Rate	20%	70%
NI Margin	20%	20%
One-sided alpha	0.025	0.025
Power	89.7%	80%
Evaluability Rate	85%	85%
N	218	218

EMA = European Medicines Agency; FDA = United States Food and Drug Administration; mITT = modified intent-to-treat; N = total sample size.

3.2. General Methods

All tables, figures, and listings will be presented in landscape orientation in Courier New, 8-point font or higher, and will be incorporated into Microsoft Word, or Adobe Acrobat PDF files, sorted and labeled according to the International Conference on Harmonisation (ICH) recommendations, and formatted to the appropriate page size(s).

Categorical parameters will be summarized using frequencies and percentages, while mean, standard deviation, median, 25th and 75th percentiles, minimum, and maximum will be used for continuous parameters.

Decimal precision will be as follows:

- Mean will contain one more decimal place than actual values.
- Median will contain one more decimal place than actual values.
- Standard deviation will contain two more decimal places than the actual values.
- 25th and 75th percentiles, minimum, and maximum will have the same precision as the actual values.

All statistical testing will be 2-sided and performed at the 0.05 level unless otherwise noted. Since no inferential testing will be conducted for secondary efficacy outcome measures, no adjustment is needed for multiplicity.

The first day of study drug administration will be Study Day 1. Subsequent study days are counted as the number of consecutive calendar days thereafter.

Individual subject listings of all data represented on the eCRFs will be provided to facilitate the investigation of tabulated values and to allow for the clinical review of all efficacy and safety parameters. All data listings and tables displaying by-subject data that contain an evaluation date will display study day (Study Day).

If a safety laboratory result is reported relative to a lower/upper range of detection for an assay, for example “<10”, the numeric portion of the result (10) will be used for statistical analyses and the full result, including any symbols, will be provided in the subject listings.

Sample sizes shown with summary statistics are the number of subjects with non-missing values. Where individual data points are missing, categorical data will be summarized based on reduced denominators (ie, only subjects with available data will be included in the denominators), unless otherwise specified.

Time-to-event data will be summarized using Kaplan-Meier methodology using 25th, 50th (median), and 75th percentiles with associated 2-sided 95% confidence intervals (CIs), as well as percentage of censored observations. The Kaplan-Meier curves will be presented by treatment group. The number of subjects at risk and number died in each treatment group will be displayed below the x-axis at day=0, 5, 14, 30, 55.

3.3. Computing Environment

All statistical analyses will be performed using SAS statistical software v9.4 or higher, unless otherwise noted.

The Analysis Data Model Version 2.1 (ADaM v2.1) and the ADaM Implementation Guide, Version 1.1 (ADaM IG v1.1) will be used for data standardization.

Medical history, concomitant procedures and AEs will be coded using the Medical Dictionary for Regulatory Activities (MedDRA) 21.0 or higher.

Prior and concomitant medications will be coded using the World Health Organization (WHO) Drug Dictionary March 2017 or higher.

3.4. Methods of Pooling Data

Data will be pooled across sites for all analyses.

3.5. Multiple Comparisons/Multiplicity

No adjustment for multiple comparison/multiplicity are to be used.

3.6. Withdrawals, Dropouts, Loss to Follow-up

Randomized subjects who are withdrawn or discontinued from the study will not be replaced.

3.7. Missing, Unused, and Spurious Data

The following rules for missing data will be followed:

- For the primary efficacy outcome measure of all-cause mortality for the FDA, subjects with a missing death date on the eCRF will be considered to have died. The subject's vital status will be determined using available sources such as the subject, the subject's contacts, hospital and other medical records and public records.
- For the primary efficacy outcome measure of global response for the EMA, subjects with a missing response are considered an indeterminate response and are included in the denominator for analyses in the mITT population.
- Adverse Event, Death Date and Prior/Concomitant Medication Date Imputations will follow the rules described in [Appendix 7 Adverse Event and Prior/Concomitant Medication Date Imputations](#).
- The CTCAE grade and causality assessment for adverse events should not be missing (except in the case of a death reported only on the Survival Status eCRF which should be considered an adverse event of Death NOS) and will be queried for a value. Should there be missing data for adverse events other than Death NOS, adverse events with missing severity will be considered severe (Grade 3) and adverse events with missing causality will be considered related to study drug. For deaths from the Survival Status eCRF (and not on the Adverse Event eCRF), missing severity will be considered Grade 5 (death) and missing causality will be considered not related to study.
- Unless otherwise specified, missing values for other individual data points will remain as missing. Missing values will not be imputed and only observed values will be used in data analyses and presentation.

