2. DEFINITIONS OF OUTCOME MEASURES

2.1. Primary Efficacy Outcome Measures

The primary efficacy outcome (for the FDA) is all-cause mortality (ACM) at Day 30 (-2 days), assessed for the mITT population. Subjects will be considered as meeting the ACM FDA endpoint at Day 30 if they have:

- a non-missing death date on the electronic case report form (eCRF), and
- study day for date of death is less than or equal to 30 days. Study Day 1 is defined as the first day of study drug administration. Subsequent study days are counted as the number of consecutive calendar days thereafter.

All attempts will be made to determine survival status at Day 30 and the Follow-up visit; subjects who complete Day 30 assessments on Day 28 or Day 29 (within the -2 days period) without further information thereafter will be considered alive at Day 30. If their status was “alive” on Day 28 or 29, and died at Day 30 their status will be “died”. However, if it is unknown whether a subject is alive or deceased (and, subsequently, a death date is also not available), the subject will be considered deceased for the primary efficacy outcome. If it is known that the subject is deceased but only a partial death date is known, imputation rules for death date as outlined in [Section 3.7](#) of this document will be followed. For the mITT population, the primary endpoint is calculated as the percentage of subjects that died out of the total number of subjects in the mITT population.

The primary efficacy outcome (for the EMA) is global cure (based on clinical cure as assessed by the Investigator, radiological cure [for qualifying invasive candidiasis subjects], and mycological eradication), confirmed by an independent DRC, at Day 14 (± 1 day) in the mITT population. A DRC that is external to the sponsor will adjudicate global response. The committee will be comprised of physicians who will determine the outcomes of each subject in a blinded fashion. The DRC determination will be utilized to determine the primary efficacy outcome.

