2.1.1. Estimand Framework

An addendum to ICH E9 introduces the concept of an estimand which translates the trial objective into a precise definition of the treatment effect that is to be estimated. The description of the estimand includes four attributes: the population, the variable (or endpoint) to be obtained for each patient, the specification of how to account for intercurrent events (ICE), and the population-level summary for the variable. These attributes are described below for the FDA and EMA primary efficacy outcomes.

Table 2-1: Estimand Attributes

	ACM at Day 30 (FDA)	Global Response at Day 14 (EMA)
Population	mITT Population (see Section 2.6)	mITT Population (see Section 2.6)
Variable/Endpoint	Deceased by Day 30	DRC global response of cure
Handling of intercurrent events	Treatment policy estimand as measured irrespective of any ICE 
 • Missing data considered deceased 	Composite estimand as the following ICE's are incorporated into the variable/endpoint: 
 • Death (failure) • Receipt of rescue therapy (failure) • Discontinuation of study drug due to an adverse event (failure) • Missing data (classified as indeterminate but analyzed as a failure)
Population-level summary	Difference between treatment groups in percentage of subjects who died	Difference between treatment groups in percentage of subjects with a DRC global response of cure

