5.8. Appendix 8: Adverse Event and Prior/Concomitant Medication Date Imputations

Adverse Event Start/Stop Date and Death Date Imputation

Imputation Rules for Partial Dates (D = day, M = month, Y = year)

Parameter	Missing	Additional Conditions	Imputation
Start date for AEs or Death Date	D	M and Y same as M and Y of first dose of test article	Date of first dose of test article
		M and/or Y not same as date of first dose of test article	First day of month
	D and M	Y same as Y of first dose of test article	Date of first dose of test article
		Y prior to Y of first dose of test article but same as Y of screening date	Date of screening date
	D, M, Y	None - date completely missing	Date of first dose of test article
Stop date for AEs	D	M and Y same as M and Y of last dose of test article	Date of last dose of test article
		M and/or Y not same as date of last dose of test article	Use last day of month
	D and M	Y same as Y of last dose of test article	Date of last dose of test article
		Y not same as Y of last dose of test article	Use Dec 31
	D, M, Y	None - date completely missing	No imputation, but assume ongoing

Note: In all cases, if an estimated start date is after a complete stop date, use the first day of the stop date month. Similarly, if the estimated stop date is before a complete or imputed start date, use the last day of the start day month. In all cases, if it cannot be determined if the adverse event occurred prior to or after the first dose of test article, the adverse event should be defined as treatment emergent.

Prior and Concomitant Medication Start Date Imputation

Parameter	Type of Medication	Imputation
Start date for con meds	Non-Antifungal	If it cannot be determined whether or not the start date of a medication (non-antifungal) is prior to the first dose of treatment, it will be assumed that the medication was received prior to the first dose of treatment
	Antifungal	Missing start dates for antifungals will be queried for a value. If it cannot be determined whether or not the start date of an antifungal is prior to the first dose of test article, it will be assumed that the medication was received prior to the first dose of treatment unless the indication notes that the medication was received after the first dose of treatment.

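### Partial death dates are imputed to the earliest candidate date with no last-known-alive limit, so a subject documented alive at Day 30 can be counted as a Day-30 death

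*SAP*

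**What the plan says.** **Endpoint (SAP Section 2.1).** A Day-30 death needs a death date on the eCRF with a study day of 30 or less. A subject without a date counts as deceased "if it is unknown whether a subject is alive or deceased". A subject whose Day 30 assessment was done on Day 28 or 29 "without further information thereafter will be considered alive at Day 30". Where death is known but "only a partial death date is known, imputation rules for death date as outlined in" Section 3.7 apply.

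**Missing data (SAP Section 3.7).** For the FDA endpoint, "subjects with a missing death date on the eCRF will be considered to have died". The next sentence reads "The subject's vital status will be determined using available sources", and lists them. Date imputation is referred to Appendix 7. That appendix is Laboratory Normals; the date rules are in Appendix 8, whose title 3.7 gives correctly.

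**Imputation (SAP Appendix 8, Section 5.8).** Death shares a row with adverse event onset: "Start date for AEs or Death Date".
- Day missing, same month and year as first dose: date of first dose.
- Day missing, otherwise: first day of the month.
- Day and month missing, same year as first dose: date of first dose.
- Whole date missing: date of first dose.

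The note's check on an estimated start date is "if an estimated start date is after a complete stop date, use the first day of the stop date month".

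**Elsewhere.** SAP Section 2.3.2 already uses the last date known alive, but only to censor survival time. Protocol Sections 10.1 and 13.10 count only unknown survival status as death, and SAP Table 2-1 has "Missing data considered deceased".

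**The concern.** Taking the earliest candidate date is a sensible convention for adverse events, because it errs towards calling an event treatment-emergent. For death, the same convention decides a binary primary endpoint. Without a last-known-alive limit, the derivation can place a death before a visit at which the subject was recorded alive, and so turn a Day-30 survivor into a Day-30 death. It would also shorten that subject's time in the Kaplan-Meier analysis of SAP Section 4.3.4.

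The rule is the same in both arms, so its direction is not fixed. False deaths in the rezafungin arm raise the upper confidence limit; false deaths in the caspofungin arm lower it. None of the three FDA sensitivity analyses in SAP Section 4.3.1.1 would show the problem: they exclude unknown status, stratify the interval, and multiply impute missing outcomes. An imputed death date is none of these.

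The Section 3.7 sentence is a separate wording matter. Taken alone it makes a missing death date a death with no condition on vital status, and every survivor lacks a death date.

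**Working it through.** **Inputs.** Rules from SAP Section 2.1 and Appendix 8. From SAP Section 3.1: 184 mITT subjects (92 per arm), 20% mortality in both arms, 20% margin, one-sided alpha 0.025. SAP Section 1.2.1/1.2.2 gives 16 August 2021 as the last randomization for the primary analysis. Assumed: first doses spread evenly over the calendar, and deaths spread evenly over Days 31–59.

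**Plan's own figure.** Power = Φ((0.20 − 1/92)/√(2 × 0.2 × 0.8/92) − 1.96) = Φ(3.207 − 1.960) = 89.4%, against 89.7% stated. The design inputs are reproduced closely enough to use below.

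**Worked cases, day of death missing.**

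| First dose | Death | Recorded as | Imputed to | Day-30 death? |
|---|---|---|---|---|
| 5 Mar 2021 | 20 Apr (Day 47) | Apr 2021 | 1 Apr = Day 28 | Yes |
| 20 Jan 2020 | 25 Feb (Day 37) | Feb 2020 | 1 Feb = Day 13 | Yes |
| 1 Mar 2021 | 10 Apr (Day 41) | Apr 2021 | 1 Apr = Day 32 | No |
| 5 Jan 2020 | 2 Mar (Day 58) | Mar 2020 | 1 Mar = Day 57 | No |

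In the first case Day 30 is 3 April. A subject seen alive that day is still counted as dead on Day 28.

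**How often, day missing.** The rule was applied to every pair of first-dose date and death day.
- First doses throughout 2021: 365 × 29 = 10,585 pairs, of which 5,366 are imputed to Day 30 or earlier. 5,366/10,585 = 50.7%.
- First doses from 1 January 2019 (assumed start) to 16 August 2021: 959 × 29 = 27,811 pairs, of which 14,180 are so imputed. 14,180/27,811 = 51.0%.
- By true death day, over the second range: 97% for Day 31, 67% for Day 40, 35% for Day 50, 5% for Day 59, 0% from Day 61.
- If deaths decline with a half-life of 20, 10 or 7 days after Day 31, the overall share is 59%, 66% or 71%.
- Mean displacement of the death date: 14.7 days earlier.

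The result is a contradiction only where the subject was documented alive on Day 30 or later. Writing q for that proportion, the wrongly counted share is q × 50.7%: 13%, 25%, 38% and 51% for q = 25%, 50%, 75% and 100%.

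**Day and month missing.** Any death in the first-dose year becomes Day 1, so it is always counted. For a death in the following calendar year the table as extracted shows no rule. Such pairs are 9.2% of those from 2019 to 16 August 2021, and none for first doses in 2021 up to that date.

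**Effect on the endpoint.** One death moves an arm's rate by 1/92 = 1.1 points. 20% of 92 is 18.4, so start from 18 deaths per arm. Unadjusted Miettinen-Nurminen 95% upper limits, rezafungin v caspofungin deaths:

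| 18 v 18 | 19 v 18 | 20 v 18 | 21 v 18 | 25 v 18 | 26 v 18 | 18 v 21 |
|---|---|---|---|---|---|---|
| 11.6% | 12.8% | 14.0% | 15.2% | 19.8% | 21.0% | 8.7% |

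The 20% margin is crossed at 26 v 18, that is 26 − 18 = 8 net false rezafungin deaths.

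**Would a bound alone be enough?** No. For a subject last seen alive on Day 30, moving the imputed date up to that contact gives Day 30, which still satisfies the endpoint definition. An explicit override is needed as well.

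**The case against.** The strongest reply is that the situation will hardly arise. The subject must be documented alive on Day 30 or later, die soon afterwards, have a partial date, and fall on the wrong side of the calendar. Deaths are serious adverse events reported within 24 hours of awareness, death certificates and autopsy reports may be requested (Protocol Section 12.3.1), and vital status is sought from hospital and public records. The documents identify no such subject. This stands, and it is why the point is minor.

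A second reply is that unknown status counts as death anyway. That also stands, for subjects not documented alive at Day 30: for them the imputed result agrees with the plan's own policy. It does not cover subjects with a survival record at Day 30.

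Three stronger readings are tempting, and the documents do not support them.
- *Survivors will be counted as dead under Section 3.7.* The next sentence of 3.7 has vital status ascertained from other sources, and SAP Section 2.1 and Protocol Sections 10.1 and 13.10 limit the rule to unknown status. The miscited appendix number comes with the right title, so it should mislead nobody.
- *Every later death with a partial date is miscounted.* With only the day missing, the imputed date must fall on or before Day 30; two of the four cases above are not counted.
- *51% is an error rate, or a general ceiling.* It is neither. It falls with the share documented alive, and rises if deaths cluster soon after Day 30.

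**Conclusion.** The point holds as a minor defect. The written rules contain no last-known-alive limit on an imputed death date and no override for documented Day-30 survival, so they can give a wrong value on the FDA primary endpoint. With only the day missing, about 51% of post-Day-30 deaths would be drawn back to Day 30 or earlier, assuming even deaths over Days 31–59 and even first-dose dates. With only the year known, and that the first-dose year, all of them would be.

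The number of partial death dates is not given, so the actual effect is unknown; it is probably very small. A reader might infer that the non-inferiority conclusion is at risk. From equal mortality at about the planned rate that would take 8 net false deaths in one arm, and nothing in the documents suggests a number of that order.

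Confidence is high on the missing bound and override. It is lower on the absent rule for a year-only date in a later year, which may be a product of text extraction.

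**What to change.** 1. **Appendix 8.** Give death its own row: the earliest date consistent with the known parts, but no earlier than the last date known alive. State that documented survival through Day 30 overrides any imputed date for the Day-30 endpoint.
2. **Section 3.7.** Replace the sentence on missing death dates with: subjects whose survival status at Day 30 is unknown will be considered deceased, subject to the Day 28/29 rule in Section 2.1.
3. **Cross-reference.** Change Appendix 7 to Appendix 8 in Section 3.7.

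Two matters are for the sponsor to settle in the same edit. One is how to classify a subject last seen alive on Day 28 or 29 whose later death is only partly dated, in a month that includes dates up to Day 30. Section 2.1's alive rule does not reach that subject, because there is later information; either classification is a policy choice and should be stated. The other is to check in the source table whether a rule exists for a year-only death date in a year after first dose, and to add one if not.

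The cost is a few lines of SAP text and one derivation rule. Survival status is already collected at Day 30 and Follow-up, and the last date known alive is already used in Section 2.3.2, so no new data are needed and the sample size does not change.

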12.5.2 Severity

All AEs will be graded for severity using the CTCAE grading criteria (version 5.0). The Investigator will assign a grade to the AE using the CTCAE definitions for Grade 1, Grade 2, Grade 3, Grade 4, or Grade 5.

Table 12: Guidelines for Severity Assessment by the CTCAE Version 5.0

	Definition
Grade 1	Mild; asymptomatic or mild symptoms; clinical or diagnostic observations only; intervention not indicated.
Grade 2	Moderate; minimal, local or noninvasive intervention indicated; limiting age appropriate instrumental ADL.
Grade 3	Severe or medically significant but not immediately life-threatening; hospitalization or prolongation of hospitalization indicated; disabling; limiting self-care ADL.
Grade 4	Life-threatening consequences; urgent intervention indicated.
Grade 5	Death related to AE.

Abbreviations: ADL = activities of daily living; AE = adverse event; CTCAE = Common Terminology Criteria for Adverse Events.

Each CTCAE term may not always be listed as expected. For example, the grading scale for pneumonia is referenced under the CTCAE term “lung infection,” for thrombocytopenia under the CTCAE term “platelet count decreased,” and for neutropenia under the CTCAE term “neutrophil count decreased.”

Each System Organ Class (SOC) category contains an “Other” option. For example, “Immune Systems Disorders Other, specify.” When a CTCAE term is not listed under the SOC category, the grading scale for the “Other” option can be referenced to aid in severity assessment.

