4.5.1. Adverse Events

Verbatim descriptions of AEs will be coded using the latest MedDRA version (version 23.0 or higher). Summary tables will be provided for all treatment-emergent adverse events (TEAEs). A TEAE is defined as an AE that occurs during or after study drug administration and up through the Follow Up visit (Days 52-59). An AE is programmatically defined as treatment emergent if the start date and time is on or after the start date and time of the first dose of study drug. If the time of an AE is missing, it is considered treatment emergent if it starts on the same date as the first dose of study drug. Date Imputations will follow the rules described in [Appendix 8 \(Section 5.8\)](#).

Deaths obtained only through the Survival Status eCRF will not be recorded on the AE eCRF, but will be programmed as an AE with SOC and PT of "Death NOS" and analyzed as an AE/SAE with outcome of fatal.

An overall summary of AEs and TEAEs will include the number and percentage of subjects in each treatment group who experienced at least 1 AE/TEAE in the following categories: any AE, any TEAE, any TEAE up through Day 7, any study drug-related TEAE, any grade 4/5 TEAE, any serious AE (SAE), any study drug-related SAE, any SAE leading to death (that includes SAE started during study with an outcome of death that occurred after the Follow-up Visit), any study drug-related SAE leading to death, any TEAE resulting in interruption of administration of study drug, any TEAE leading to discontinuation of study drug, and any TEAE resulting in study discontinuation. The overall summary of AEs will be repeated for the high risk subgroups defined in [Table 4-1](#).

Subjects with multiple events will be counted only once within each category. CTCAE grade (version 5.0) and relationship will be counted using the maximum grade and the strongest relationship respectively for a subject with multiple TEAEs.

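### An adverse event with a recorded fatal outcome but no severity grade after query would be imputed as Grade 3, against the protocol's Grade 5 definition and the SAP's own rule for survival-form deaths

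*SAP*

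**What the plan says.** SAP 3.7 expects a CTCAE grade for every adverse event and says that a missing one should not occur "and will be queried for a value". For grades that stay missing it has two rules in one bullet.

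- Events on the Adverse Event eCRF: "Should there be missing data for adverse events other than Death NOS, adverse events with missing severity will be considered severe (Grade 3". The only exemption is Death NOS.
- Deaths on the survival form only: "For deaths from the Survival Status eCRF (and not on the Adverse Event eCRF), missing severity will be considered Grade 5 (death".

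SAP 4.5.1 explains that Death NOS is a programmed term for deaths found through the Survival Status eCRF alone. A death entered on the AE form under its own diagnosis is not Death NOS, so the first rule covers it.

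Protocol 12.5.2, Table 12, defines Grade 5 as "Death related to AE", Grade 4 as life-threatening, and Grade 3 as severe without immediate threat to life.

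Two outputs in SAP 4.5.1 use the grade: the overall summary has a row for "any grade 4/5 TEAE", and TEAEs are tabulated by system organ class, preferred term and maximum grade from 1 to 5. Separately, SAEs leading to death appear in the overall summary, and fatal SAEs are tabulated by class and term. Both of these depend on outcome, not grade.

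**The concern.** For an event whose recorded outcome is death, the severity field is blank but the information that decides the grade is not. Imputing Grade 3 overrides a known fact with a value that excludes it. The SAP already accepts that a known death means Grade 5, but applies this only to deaths that never reached the AE form.

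What is at stake is the agreement of the safety tables. A grade-based table and an outcome-based table drawn from the same data could give different numbers of fatal events, and for these events the difference lowers the most severe category. That sits badly with the evident caution of the bullet, which treats missing causality on the AE form as related to study drug.

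**Working it through.** The plan states no figure on this point, so there is none to reproduce. The check traces the rule through the outputs and then sizes one affected subject.

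**Tracing the rule.** In each row the grade is taken as still missing after the query.

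| Record | Imputed grade (SAP 3.7) | Grade 4/5 row of overall summary | Maximum-grade table | Fatal-SAE tables |
|---|---|---|---|---|
| (a) AE eCRF, outcome fatal | 3 | Not counted through this event | Grade 3 | Counted |
| (b) Death on Survival Status eCRF only | 5 | Counted | Grade 5 | Counted |
| (c) AE eCRF, life-threatening, not fatal | 3 | Not counted through this event | Grade 3 | Not applicable |

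Rows (a) and (b) both describe a known death, but they receive different grades. Row (a) conflicts with the Table 12 definition of Grade 5, and row (c) with its definition of Grade 4.

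**Looking for an override.** Protocol 12.5.2 asks the Investigator to assign a grade and says nothing about imputation. SAP 4.5.1 does not modify the 3.7 rule. SAP Appendix 6 grades laboratory values only, and Appendix 8 imputes dates only. None of these restores Grade 5 in row (a).

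**How counting limits the effect.** SAP 4.5.1 counts a subject once per category at the maximum grade. In the Grade 4/5 row, a subject with any other Grade 4 or 5 TEAE is therefore still counted. In the maximum-grade table, a preferred term reported more than once is shown at its highest grade. The row changes only for a subject whose sole Grade 4/5 event is the ungraded one.

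**Size per affected subject.** The plan randomizes about 218 subjects 1:1, which is 218/2 = 109 per arm, and targets 184 in the mITT population, which is 184/2 = 92 per arm. mITT membership requires at least one dose, so with the planned numbers split evenly the Safety population lies between 92 and 109 per arm.

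- 1/109 = 0.0092, or 0.9 percentage points.
- 1/92 = 0.0109, or 1.1 percentage points.

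The number of such subjects cannot be derived, because the documents give no rate of grades missing after query.

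**Is the needed information available?** SAP 4.5.1 tabulates fatal SAEs and SAEs with an outcome of death, so outcome must be in the analysis data. The life-threatening criterion is less certain: Protocol 12.2 lists only seriousness among the items on the AE eCRF page, and the specific criterion is requested on the serious adverse event report (Protocol 12.3.1).

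**The case against.** The strongest reply is that the situation should hardly arise. SAP 3.7 says the grade should not be missing and is queried. The Investigator grades every event (Protocol 12.5.2). A fatal or life-threatening event is an SAE (12.4.4), its report asks for severity again (12.3.1), and the Investigator signs the eCRF only once queries are resolved (14.2). Fatal events are therefore among the least likely to stay ungraded. This stands, and it is why the point is minor.

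It can also be said that the two rules serve different purposes. Grade 5 fills a structural gap for survival-form deaths, where no grade is expected, while Grade 3 is a general fallback for a required field. That explains how the wording came about, but it does not make Grade 3 right for a known death.

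Three stronger readings are tempting but not supported:

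- A reader might infer that fatal events disappear from the safety report. They do not: the outcome-based summaries, tables and listings in SAP 4.5.1 still carry them.
- A reader might infer that the rule understates severity in general. For an ungraded event that was truly Grade 1 or 2 it overstates severity. The understatement is confined to events that were fatal or life-threatening.
- A reader might multiply the planned 20% mortality by a guessed missing-grade rate to get a count per arm. The documents contain no such rate. The 20% is a Day 30 planning assumption for the mITT population, in an endpoint that counts unknown survival status as death, and some deaths may be recorded on the survival form only. It is not a count of fatal events on the AE form.

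**Conclusion.** The rule is wrong as written for an AE-form event with a recorded fatal outcome. It contradicts Protocol Table 12, departs from the rule the same bullet applies to survival-form deaths, and lets the grade-based and fatal-SAE tables disagree. For life-threatening events the conflict with Table 12 is equally clear, but the remedy depends on a data item the documents do not show to be in the analysis data.

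The practical effect is small: probably few events or none, each worth about 0.9 to 1.1 percentage points in one arm's Grade 4/5 incidence if the subject has no other such event. This range assumes the planned arm sizes and an even split. No efficacy analysis or hypothesis test uses adverse event grade. The correction is worth making because it is cheap and removes a conflict between tables that otherwise depends on every query succeeding.

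**What to change.** Amend the sentence in SAP 3.7 so that severity still missing after query is imputed as follows:

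- Grade 5 when the recorded outcome is fatal, whichever form recorded the death.
- Grade 4 when the event is recorded as life-threatening, provided that seriousness criterion is available in the analysis data.
- Grade 3 otherwise.

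If the life-threatening criterion is held only in the safety reporting system, the second line should be dropped or the item brought into the analysis data first. A footnote giving the number of imputed grades per arm would show the reader how often the rule was used.

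The cost is one SAP sentence and a short derivation from the outcome the SAP already tabulates. SAP 1.1.1 provides for a SAP amendment if the change is made before database lock, and for a description in the clinical study report if it is made afterwards. No new data collection is needed for the fatal-outcome part.
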